# Spatz 3 US Pivotal Trial Protocol

Protocol Version	V1.4e (January 11, 2017)
Sponsor	Spatz FGIA [name] Contact Person: [name] CEO, Spatz FGIA, Inc [contact]
Trial Title	A randomized, controlled, multicenter study comparing the Spatz3 Adjustable Balloon System plus diet and exercise to diet and exercise alone.
Device Name	Spatz3 Adjustable Balloon System® (Spatz3)
Clinical Phase	Pivotal
Trial Design	Multicenter open-label randomized controlled trial
Trial Participants	Adults with a BMI $\geq$ 30 and $<$ 40 who have failed to achieve and maintain weight-loss with a weight control program
Control group	Supervised diet and exercise
Planned sample size	282 subjects randomized 2:1 to device/control
Follow-up duration	8 months for control and 14 months for treatment
Planned trial period	30 months
Primary endpoints	Percent change in total body weight (%TBL) at 32 weeks AND Clinical response, where a responder is defined as a subject with at least a 5% loss in total body weight at 32 weeks
Secondary endpoints	Maintenance of 40% of the weight loss with the balloon six months after the balloon is removed Clinical response, where a responder is defined as a subject with at least a 25% loss in excess body weight at 32 weeks

## **LIST OF PROTOCOL APPENDICES**

A – Informed Consent

B – Study Visits and Master Schedule

C – Spatz3 Clinical Study: Diet and Exercise Plan – Treatment and Control

D – Spatz3 Clinical Study: Physical Exercise Program – Treatment and Control

E – Case Report Forms:

E1: CRF1\_Treatment / Control Group Assignment and Baseline Weight

E2: CRF2\_Pi Intake

E3: CRF3\_Screening Labs

E4: CRF4\_Pre-implantation Tests and Data

E5: CRF5\_Dietician Intake

E6: CRF6\_Control Group PI Follow Up Visits

E7: CRF7\_Treatment Group PI Follow Up Visits

E8: CRF8\_Control Group Dietician Follow Up Visits

E9: CRF9\_Treatment Group Dietician Follow Up Visits

E10: CRF10\_Consultation with Psychologist

E11: CRF11\_Diabetic Patient Follow Up

E12: CRF12\_Adverse Events

E13: CRF13\_Baseline and Follow-up Weights

## **1. ADMINISTRATIVE INFORMATION**

### **1.1. Title**

A randomized, controlled, multi-center study comparing the Spatz3 Adjustable Balloon System plus diet and exercise to diet and exercise alone.

### **1.2. Trial Registration**

This trial protocol has been registered with [clinicaltrials.gov](http://clinicaltrials.gov).

### **1.3. Protocol Version**

**Version number:** V1.4e

**Issue date:** January 11, 2017

### **1.5. Roles and Responsibilities**

#### **1.5.1. Sponsor Responsibility**

The sponsor has the following responsibilities:

- **FDA and IRB approval**
  - The sponsor will not begin this study (or any significant change to this study) until an IRB and FDA have both approved the application or supplemental application.
- **Selecting Investigators**
  - The sponsor is responsible for selecting investigators qualified by training and experience to investigate the device. The sponsor will supply all investigators participating in the investigation with copies of the investigational plan and a report of prior investigations of the device.
- **Investigator Agreement**
  - The sponsor will obtain a signed agreement from each participating investigator that includes:

- The investigator's curriculum vitae,
  - A statement of the investigator's relevant experience, including the dates, location, extent, and type of experience, where applicable,
  - An explanation of the circumstances that led to termination of a study if the investigator was involved in an investigation or other research that was terminated,
  - A statement of the investigator's commitment to:
    - Conduct the investigation in accordance with the agreement, the investigational plan, the IDE and other applicable FDA regulations, and conditions of approval imposed by the reviewing IRB or FDA,
    - Supervise all testing of the device involving human subjects
    - Ensure that the requirements for obtaining informed consent are met.
    - Sufficient accurate financial disclosure information to allow a sponsor to submit a complete and accurate certification or disclosure statement as required under 21 CFR 54, Financial Disclosure by Clinical Investigators. A sponsor shall also obtain a commitment from the clinical investigator to promptly update this information if any relevant changes occur during the course of the investigation and for one year following completion of the study.
- **Monitoring**

The study will be monitored by the Clinical Research Organization, Clinical Development Associates Inc. (see Section 9 below).

    - *Securing Compliance*: If the sponsor discovers that an investigator is not complying with the signed agreement, the investigational plan, the IDE requirements, any other applicable FDA regulations, or any conditions of approval imposed by the reviewing IRB or FDA, then the sponsor will promptly either secure compliance, or discontinue shipments of the device to the investigator and terminate the investigator's participation in the investigation. The sponsor will also require that the investigator dispose of or return the device, unless this action would jeopardize the rights, safety, or welfare of a subject.
    - *Unanticipated Adverse Device Effects*: The sponsor will immediately conduct an evaluation of any unanticipated adverse device effect. If the sponsor determines that an unanticipated adverse device effect presents an unreasonable risk to subjects, then they must terminate all investigations or parts of the investigations presenting that risk as soon as possible. Termination will occur no later than 5 working days after the sponsor makes this determination and no later than 15 working days after the sponsor first received notice of the effect.
    - *Resumption of Terminated Studies*: The sponsor will not resume a terminated investigation without IRB and FDA approval.
  - **Sponsor Records (§ 812.140)**

- The sponsor will maintain accurate and complete records relating to the investigation. These records include:
  - All correspondence including required reports,
  - Records of shipment of the device,
  - Records of disposition of the device
  - Signed investigator agreements including financial disclosure information,
  - Records concerning complaints and adverse device effects whether anticipated or not,
  - Any other records that FDA requires to be maintained by regulation or by specific requirement for a category of investigation or a particular investigation.
- **Device Control**
  - The sponsor will ship investigational devices **only** to qualified investigators participating in the investigation.

### 1.5.2. Investigators

One investigator per contributing site will be nominated as a local coordinator.

Investigator responsibilities will include:

- The investigator is responsible for protecting the rights, safety, and welfare of subjects. An investigator must conduct the investigation in accordance with the signed agreement with the sponsor, the investigational plan, the IDE regulations and other applicable FDA regulations, and any conditions of approval imposed by an IRB and FDA.
- While awaiting approval of an IDE application, an investigator may determine whether or not potential subjects would be interested in participating in an investigation, but cannot request written informed consent or allow any subjects to participate before obtaining IRB and FDA approval.
- An investigator is responsible for obtaining informed consent from all study subjects.
- An investigator agrees to use the investigational device only with subjects under his/her supervision and will not supply an investigational device to any person not authorized under the IDE regulations to receive it.
- **Financial Disclosure**
  - The clinical investigator must disclose to the sponsor sufficient accurate financial information to allow the IDE applicant (or sponsor) to submit certification or disclosure of financial interests under 21 CFR 54. The investigator must update the information if any relevant changes occur during the course of the investigation and for one year following completion of the study.

- **Device Disposal**

- Upon completion or termination of a clinical investigation or the investigator's part of the investigation or at the sponsor's request, an investigator must return to the sponsor any remaining supply of the device or dispose of the device as the sponsor directs.

- **Records**

The investigator must maintain accurate and complete records relating to the investigation. These records include:

- All correspondence including required reports,
- Records of receipt, use, or disposition of the investigational device,
- Records of each subject's case history and exposure to the device,
- The protocol and documentation (date and reason) for each deviation from the protocol,
- Any other records that FDA requires to be maintained by regulation or by specific requirement for a category of investigation or a particular investigation.

### **1.5.3. Data Monitoring Committee**

The Data Monitoring Committee is responsible for:

- Preparing a charter for the conduct of the committee
- Reviewing data from the study according to the schedule set out in the protocol
- Reviewing adverse events to determine if they are serious adverse events and if they are device related and evaluating any device deficiencies

## 2. INTRODUCTION

### 2.1. Background

Obesity in the United States has been increasingly cited as a major health issue in recent decades. Like the U.S., many industrialized countries have experienced similar increases, underscoring the severity of the problem. The United States had the highest rate of obesity for large countries (> 32%), until obesity rates in Mexico surpassed that of the United States in 2013[1]. Childhood obesity has more than doubled in children and quadrupled in adolescents in the past 30 years [1].

The American Heart Association (AHA) notes that 60-70% of the US population is either overweight or obese, putting them at risk for heart disease, stroke, high blood pressure and diabetes. According to the AHA, obesity affects nearly 78 million adults and 13 million children in the US today. The CDC found there was no decrease in obesity rate from the 2009-2010 survey to the 2011-2012 survey [3].

Among Americans age 20 and older, 154.7 million are overweight or obese (BMI of 25.0 kg/m^2 and higher): - 79.9 million men and 74.8 million women. Of these 154.7 M, 78.4 million are obese (BMI of 30.0 kg/m^2 and higher): 36.8 million men and 41.6 million women. If current trends in the growth of obesity continue, total healthcare costs attributable to obesity could reach \$861 to \$957 billion by 2030, which would account for 16% to 18% of US health expenditures (AHA) [3].

To date, treatment options for the US obese population include weight loss management programs, pharmaceuticals, and bariatric surgeries (gastric bypass, sleeve gastrectomy and gastric banding accounting for 99% of the bariatric surgeries) [4]. FDA has also recently approved the Enteromedics vagal nerve stimulator and the Orbera intragastric balloon and the Reshape Duo intragastric balloon, but it is too soon to assess the potential impact of these therapies.

### 2.2. Current Treatment Options

Unfortunately, the results of most weight loss management programs are rather dismal. Efficacy of behavioral changes is dependent on both a highly motivated subject and a dedicated counselor willing to maintain long-term follow-up. On average, the best weight loss programs achieve approximately 10% body weight loss, with patients compliant to diet only 20% of the time [5].

Belviq, a serotonin enhancing drug, is available in the US market and has 3-3.7% weight loss in one year. Side effects of paresthesias, fatigue, headache and dizziness have been reported. Qsymia is a combination drug containing the appetite suppressant phentermine and the seizure medicine Topiramate. 38% of users have reported weight loss of 105 or greater. Long term follow up studies to evaluate weight loss maintenance are not available in either drug [6]. Previously approved drugs include, Orlistat, which inhibits fat absorption in the intestine; Phentermine, Methamphetamine, Benzphetamine, Diethylpropion, and Phendimetrazine, which are appetite suppressants and DEA scheduled drugs [7].

Surgical therapy for obesity (bariatric surgery) is the only available therapeutic modality in the US associated with significant and sustained weight loss in the setting of subjects with morbid obesity associated with co-morbidities. Evidence is available to show that well-performed bariatric surgery in the setting of carefully selected patients and a good multidisciplinary

support team significantly ameliorates the morbidities associated with severe obesity. While bariatric surgery is the only therapeutic method associated with consistently demonstrable sustained weight loss, it is expensive, highly procedure-specific and surgeon-specific, and certainly not the only solution for the burgeoning obesity epidemic.

Among the standard bariatric procedures are roux-en-Y gastric bypass, sleeve gastrectomy and gastric banding surgeries. Gastric bypass surgeries have been available for many years and have evolved and improved, but reported mortality rates of 0.5% [8] have left a 0.6% penetration into the eligible population [9]. Reports in 16,000 Medicare beneficiaries who received roux-en-y gastric bypass surgery between 1997-2002, revealed mortalities of 2% at 30 days and 4.6% at one-year post operatively [10]. An 8-20% post-operative infection rate has led to a 25% re-operation rate within 3-5 years. As a result of these statistics, the growing population of morbidly obese patients is met with diminishing therapeutic options. Furthermore, a review of 60,000 Medicare patients who underwent roux-en-y gastric bypass surgery from 1995-2004, revealed a fourfold increase in medical expenditures in the 3-year post-op compared with the 3-year pre-op (not including the cost of surgery) [11].

Gastric banding consists of a silicone elastomer band that is placed around the upper part of the stomach to create a small stomach pouch, which can hold only a small amount of food. The diameter of the band outlet is adjustable to meet individual needs, which can change as one loses weight. Disadvantages of gastric banding include balloon leakage, band erosion/migration, band slippage, and reservoir leakage [12]. The negative impact of mortality figures and economic figures, have led the medical community to seek non-surgical bariatric solutions.

### **Intragastric Balloons**

Intragastric Balloons (IGBs) were introduced decades ago as a minimally invasive treatment for morbid obesity. Gastric balloons fill the stomach to induce a feeling of satiety and are effective in achieving weight reduction [14 - 40]. In the 1980's the Garren-Edwards bubble for weight loss was removed from the US market due to life threatening complications of bowel obstruction from deflated bubbles (balloons). This prompted the Tarpon Springs comprehensive workshop in 1987 that delineated new standards for intragastric balloons: smooth, seamless balloons, fluid filled, adjustable, and with radio-opaque markers [13]. The next generation of IGBs, led by the BIB balloon (Bioenterics intragastric balloon) meets most of those requirements, with the exception of adjustability, and have been used OUS for the last 25 years. In the summer of 2015 both the Orbera and Reshape balloons were granted PMA approval by the FDA. These intragastric balloons are indicated for adults > 18 yrs old (or > 21 yrs old for Reshape Duo) as an adjunct to weight loss for those with BMI  $\geq 30$  and < 40 in individuals who have failed conventional weight loss therapy.

IGBs are silicone spheres filled with saline that sit in the stomach for 6 months taking up stomach volume, delaying stomach emptying and thereby decreasing appetite and preventing overeating. The deployment requires a routine endoscopy under conscious sedation which is done to be certain there are no lesions that would preclude use of the balloon. The Orbera and Re-Shape balloons are inflated at the implantation procedure and this volume remains stagnant until extraction. After 6 months, the IGBs are removed by piercing and draining balloon, and the balloon is then removed by a snare or grasping forceps. Behavior modification therapy prior, during and after balloon deployment as well as an exercise program is an essential part of the treatment.

The literature is filled with publications of the successful use of intragastric balloons outside of the US with wide ranging reports of 12-21 kg weight loss and 20-38 % EWL over 6 months, and with complication rates of up to 5 % [14 - 38]. Due to the wide range of published results, two comprehensive reviews of the BIB literature have been published in 2008 that meticulously scrutinized publications and chose studies based on multiple criteria such as controlled trials, randomization, low dropout rate, consecutive patients in series, etc [39,39]. Both review articles concluded that intragastric balloons are a “valuable” or “effective” non-surgical therapy for weight loss. Weight losses of approximately 8 to 16 kg, with 12% to 15 % weight loss and 20-30% EWL were noted in these “approved” studies. The reviewers reported 4.2% to 6.7% early balloon removals and an 8.1% deflation rate with 5 cases requiring surgery (4.1%). Studies have shown that a greater than 10% weight loss can prevent and reduce cardiovascular risks and other obesity-related diseases [41,41]. In the recently published FDA trials, the Reshape and Orbera reached their endpoints with  $\geq 25\%$  EWL in over 35% of treatment subjects with a superiority margin of  $> 7.5\%$  compared with control arm subjects (sham control in the Reshape trial and diet/exercise control in the Orbera trial). In the Reshape Duo balloon SSED published by the FDA the mean weight loss was 14.3 lbs/6 months with 25.1% EWL and 6.8% TBL compared with 11.3% EWL; 3.3% TBL and 7.2 lb weight loss in the control arm. Adverse events included nausea and vomiting in 85% of patients in the first 3 days post implantation. There were 7.5% serious adverse events requiring early device removal. 39.6% ulcerations were reported, however, following design change the ulceration rate fell to 10.3%. There was one episode of UGI hemorrhage from a gastric ulcer. The extraction procedure caused one contained esophageal perforation and one esophageal tear that was closed with endoscopic clips.

In the Orbera balloon SSED published by the FDA the mean weight loss was 16 lbs/6 months with 29 % EWL and 7.6 % TBL compared with 11.1% EWL; 3.1 % TBL and 6 lb weight loss in the control arm. Adverse events included nausea and vomiting in 85% of patients in the first 3 days post implantation. There were 5.6 % serious adverse events requiring early device removal including a gastric perforation leading to sepsis and surgery.

In 1987 the Tarpon Springs comprehensive workshop on endoscopic therapy for weight loss delineated standards for IGBs: a) smooth balloon surface, b) fluid filled, c) adjustable, and d) with radio-opaque markers [13]. Unlike any other IGBs that are currently commercially available in the world, including the BIB (Orbera), Reshape Duo, Medsil, Silimed, and Medicone balloons, the Spatz3 device is the only intragastric balloon that meets all of those requirements.

### **3. STUDY DESIGN**

#### **3.1. Study Hypothesis**

Patients who receive the Spatz3 balloon for 8 months will lose significantly more weight than those treated with diet and exercise alone.

#### **3.2. Endpoints**

##### **3.2.1. Effectiveness**

There are two co-primary effectiveness endpoints:

- Percent change in total body weight (%TBL) at 32 weeks; and
- Clinical response, where a responder is defined as a subject with at least a 5% loss in total body weight at 32 weeks

There are two secondary endpoints:

- Maintenance of 40% of the total body weight loss with the balloon six months after the balloon is removed
- Clinical response, where a responder is defined as a subject with at least a 25% loss in excess body weight at 32 weeks

##### **3.2.2. Safety**

The incidence, frequency, and severity of adverse events related to treatment with the device will be reported.

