#### **4.3.3.2.3. Medications**

All treatment arm subjects will receive the following oral medications for the implantation and upward adjustment procedures:

- Aprepitant (Emend) [implantation procedure only] 125 mg immediately prior to or 1 hour after the procedure, 80 mg the morning after the procedure and another 80 mg two mornings after the procedure.
- Ondansetron 8 mg will be taken every 6 hours starting 1 hour after the procedure for 12 tablets (3-4 days);
- Hyoscyamine 0.125 mg prn for abdominal pain or spasm 1-2 tablets every 4 hours sublingually (maximum 12 tablets/ 24 hours)
- Percocet 10 mg will be provided for subjects who have abdominal pain that is not relieved by Hyoscyamine.
- A PPI (proton pump inhibitor such as Nexium 20 mg, Protonix 40 mg or Prevacid 30 mg) will be taken daily for the entire 8 months to reduce acid in the stomach. This helps preserve the silicone and also controls acid reflux symptoms, should they arise.
- Probiotic, Acidophilus, 8-10 Billion CFU will be taken once daily for the 8-month period.

During the 8-month implantation period, different symptoms may arise such as constipation, nausea, vomiting, bloating, abdominal pressure, heartburn, and diarrhea. These can be treated as discussed below.

Constipation is expected in the first week after implantation. It generally resolves after oral intake increases in the first 2 weeks. If it persists, standard treatments such as a teaspoon of mineral oil daily, Milk of Magnesia, or Miralax (OTC med) 17 gram+ 8 oz water twice daily.

Nausea and/or vomiting or bloating or abdominal pressure can be treated with metoclopramide – 10 mg orally up to 4 times in 24 hours.

Heartburn can be treated by increasing the PPI medication to twice daily; addition of antacids such as Maalox, Mylanta, Gaviscon – 30 ml or 2 tablets every 3-4 hours; or addition of Sucralfate suspension 1,000 mg 4 times daily

Diarrhea is expected in about 20-25% of patients and is due to a mild case of bacterial overgrowth in the stomach and small intestine. Should diarrhea develop, the probiotic Acidophilus will be increased to 4 pills daily for 4 days and during those 4 days the PPI will not be taken. In the event those measures do not alleviate the diarrhea, treatment with Metronidazole 500 mg 3 times daily for 5 days will commence - generally the diarrhea improves on the first day of treatment. Some subjects have recurrence and require repeat treatment.

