### **Severity Definitions**

The following definitions will be used to determine the severity rating for all adverse events:

Mild: awareness of signs or symptoms, that does not interfere with the subject's usual activity or is transient that resolved without treatment and with no sequelae.

Moderate: a sign or symptom, which interferes with the subject's usual activity.

Severe: incapacity with inability to do work or perform usual activities.

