**6.2.3. Procedures for recording adverse events**

It is the responsibility of the local investigator to ensure that all adverse events (AEs, ADEs, and device deficiencies) occurring during the course of the study are recorded. This may include but not be limited to:

- A description of the event
- The dates of the onset and resolution
- Action taken
- Outcome
- Initial assessment of relatedness to the device (final adjudication will be made by the DMC)
  - a. Whether the AE is serious or not
  - b. Whether the AE arises from device deficiency
  - c. Whether the AE arises from user error

Adverse events that occur during the course of the study should be treated by established standards of care that will protect the life and health of the study subjects

It is the responsibility of the local investigator to collect all directly observed adverse events and all adverse events spontaneously reported by the subject. In addition, each subject should be questioned about adverse events at each visit. Adverse events should be recorded on provided serious adverse event data collection forms.

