#### **7.3. Safety**

All adverse events and all serious adverse events will be summarized by treatment group as the first occurrence for each subject. These adverse events will also be presented by causality. In addition, the number and percent of subjects with balloon deflation will be summarized.

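### The safety endpoint promises incidence, frequency and severity of adverse events, but the counting rule in section 7.3 yields incidence only

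*Combined protocol and SAP*

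**What the plan says.** The whole safety endpoint is one sentence in section 3.2.2: "The incidence, frequency, and severity of adverse events related to treatment with the device will be reported".

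Section 7.3 gives the analysis in three sentences:
- the counting rule: "All adverse events and all serious adverse events will be summarized by treatment group as the first occurrence for each subject";
- one breakdown: "These adverse events will also be presented by causality";
- one device-specific count: "the number and percent of subjects with balloon deflation will be summarized".

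Data collection is broader than this. Section 6.2.1 grades every event: "The following definitions will be used to determine the severity rating for all adverse events" (mild, moderate, severe). Section 6.2.3 lists onset and resolution dates among the items to record and says that "each subject should be questioned about adverse events at each visit".

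The protocol also expects repeat events. On diarrhea, section 4.3.3.2.3 says "Some subjects have recurrence and require repeat treatment", and Table 1 in section 6.2.2 also notes that it can come back. Section 4.3.3.2.3 prescribes the symptom medication (apart from one antiemetic kept for implantation) for upward adjustment as well as implantation. Section 4.3.3.2.8 refers to acute accommodative symptoms after both placement and adjustment.

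Section 7.1.4 plans an adverse event analysis by how many adjustments a subject had and by balloon volume. It states no rule for counting events or grading severity.

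**The concern.** A summary by first occurrence counts subjects with at least one event. That is a sound and usual way to report incidence, but it is not frequency, and it says nothing about severity. Section 7.3 names no other way of counting adverse events, so the stated method does not produce the stated endpoint.

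The gap matters most around the volume adjustment, which section 2.2 presents as a feature that sets this device apart from other balloons. A subject with nausea at implantation has already used up the first occurrence. Under the rule in 7.3, nausea that returns after volume is added at about week 18 adds nothing to the summary. If the section 7.1.4 analysis inherits the same rule, a pre-adjustment episode could also be tabulated under the higher-volume group that the subject later joins.

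**Working it through.** **Endpoint against analysis.**

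| Promised in 3.2.2 | Specified in 7.3 | Delivered? |
|---|---|---|
| Incidence | Subjects with a first occurrence, by group and by causality | Yes |
| Frequency | No event count, no rate per subject or per time | No |
| Severity | No table by first, worst or each episode | No |

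The other sections that touch adverse events do not fill the gap:
- 4.3.3.2.7 counts device failures.
- 6.1 and 6.3.2 follow time to a subject's gastric ulcer.
- 7.1.4 has no counting rule.

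**What a later, worse episode does under the rule.**
- Mild first, then serious: the second episode appears in the serious adverse event summary as that subject's first serious event.
- Mild first, then severe but not serious: the subject is already counted, and no table shows the grade.

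**Size, illustrated with diarrhea.** The plan states no figure to reproduce. Inputs from the documents are 188 device subjects (section 3.3), a diarrhea rate of 20% (Table 1) and a range of 20 to 25% (section 4.3.3.2.3). Recurrences per affected subject, r, are not given; 0.25 to 1 is an assumption.

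Uncounted episodes = 188 × rate × r. Share of all episodes uncounted = r / (1 + r).

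| r (assumed) | 20%: 37.6 subjects | 25%: 47 subjects | Share uncounted |
|---|---|---|---|
| 0.25 | 9.4 | 11.8 | 20% |
| 0.5 | 18.8 | 23.5 | 33% |
| 1 | 37.6 | 47 | 50% |

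**Why a severity table should use the worst episode, not the first.** Suppose each episode is severe with probability q, independently, and a fraction f of affected subjects has a second episode. The share of ever-severe subjects missed by grading only the first is 1 − q / [q + (1 − q) f q] = 1 − 1 / [1 + (1 − q) f].
- q = 0.20, f = 0.25: 1 − 1/1.20 = 17%.
- q = 0.05, f = 0.50: 1 − 1/1.475 = 32%.

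Both q and f are assumed; the documents give neither.

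**The case against.** The best defense is that section 3.2.2 is itself a commitment to report all three quantities, and that 7.3 never says its first-occurrence summary is the only one. Subjects are asked about events at each visit, severity is graded for all events, and nothing is discarded from the data. Serious events are summarized in their own right. Serious and device-related events go to the sponsor within 24 hours (section 6.2.4), the monitoring committee adjudicates events, and ulcers have their own rule. Safety carries no hypothesis test.

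Most of this stands, and it limits the point. A reader might infer that repeat events are lost altogether, or that a later serious episode would be hidden; the documents support neither. A reader might also infer that severity will be tabulated at first occurrence, but 7.3 plans no severity table of any kind.

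It is also tempting to apply the 85% nausea and vomiting rate in section 2.2 to 188 subjects (0.85 × 188 = about 160) and treat nearly all post-adjustment nausea as uncounted. That does not follow. The 85% comes from two other balloons whose volume is not adjusted. The 188 are randomized subjects, and some will not be implanted (sections 3.3 and 7.1.1). Not all of those implanted receive an upward adjustment (section 4.3.3.2.5). The 160 would be subjects with a first event, not missed events, and no section gives a symptom rate after adjustment.

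The defense does not supply a method. Section 3.2.2 says frequency and severity will be reported but not how, and the one counting rule written down yields neither. Section 7.1.4 addresses adjustment but leaves the counting open.

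**Conclusion.** The point holds as a mismatch between endpoint and analysis. Section 7.3 specifies a summary for one of three promised quantities. Repeat events, and later episodes that are severe but not serious, would be recorded but absent from the planned summary.

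The wording is also open: first occurrence could mean the first of each event term or a subject's first event of any kind. On the second reading, different later events would go uncounted too.

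The size cannot be fixed from the documents. For diarrhea alone, the illustration gives about 9 to 38 uncounted episodes at a 20% rate and about 12 to 47 at 25%. It rests on an assumed 0.25 to 1 recurrence per affected subject and on all 188 device subjects being implanted. The primary effectiveness conclusions are unaffected. This should be corrected, and the counting rules are best fixed before the data are seen.

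**What to change.** In section 7.3:
1. Keep the first-occurrence summary as the incidence table, and state that it applies per event term.
2. Add, by event term and treatment group, the total number of events. Because control subjects are followed for 32 weeks and device subjects for 32 + 24 = 56, give the comparison over a common period or per subject-time.
3. Add the number of subjects by worst severity for each event term.
4. Produce these for all adverse events, serious adverse events and device-related adverse events.

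In section 7.1.4, state that the adverse event analysis by adjustment counts events by onset date relative to the adjustment, so that symptoms returning after a volume change are counted there and earlier ones are not.

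The cost is a few lines of text and a few more tables. Severity grades, event dates and visit-by-visit questioning are already in the protocol, so no new data or visits are needed.
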